#### PMTCT Motivation

For each of the following, indicate the extent to which you agree or disagree with the statement.

SD=strongly disagree, D=disagree, N=neither agree nor disagree, A= agree, SA = strongly agree.

|   | SD | D | N | A | SA |
|---|----|---|---|---|----|
| 28. I know I can maintain perfect adherence to my medication while my baby is very young and breastfeeding.                       |    |   |   |   |    |
| 29. Giving my baby his/her medication is extremely important to his health  |    |   |   |   |    |
| 30. Even if s/he does not want to take it, I know that I'll be able to give every dose of his/her medication                      |    |   |   |   |    |
| 31. It is extremely important to get routine viral load tests while my baby is still breastfeeding.                               |    |   |   |   |    |
| 32. Other commitments – such as work, household duties, childcare – may prevent me from getting my baby tested by 6 weeks of age. |    |   |   |   |    |
| 33. Attending all of my child's appointments is extremely important to me.  |    |   |   |   |    |

#### COVID-related questions

Please indicated the degree to which you expect COVID-19 to impact the following events.

|  | Strongly Disagree | Disagree | Neutral | Agree | Strongly Agree |
|--|-------------------|----------|---------|-------|----------------|
| 45. I was worried that delivering in a hospital would expose me and my child to COVID-19   |                   |          |         |       |                |
| 46. I am worried that attending the hospital for infant testing will expose me and my child to COVID-19  |                   |          |         |       |                |
| 47. During pregnancy, challenges with travel to and from the hospital (cost and/or availability of cars) as a result of COVID-19 caused me to delay or miss attending some ANC or medication refill appointments |                   |          |         |       |                |
| 48. During pregnancy, I delayed or missed ANC or medication refill appointments because I was feeling unwell and did not want to risk exposing others to illness.  |                   |          |         |       |                |

#### ENGAGEMENT WITH HITSYSTEM - INTERVENTION ONLY

49. Since enrolling in ANC, have you received any SMS from the hospital?

- a. No, I have not received any SMS.
- b. Yes, I have received at least one SMS from the hospital but less than 3
- c. Yes, I have received between 3 and 5 SMS
- d. Yes, I have received more than 5 SMS

50. Have you received an SMS for any of the following reasons?

- a. To check how you are doing..... Yes / No
- b. To inform you of your next appointment date..... Yes / No
- c. To remind you to take ART medications..... Yes / No
- d. To let you know your child was due for services..... Yes / No
- e. Asking you to return to the hospital to be informed of a test result..... Yes / No

51. If yes to any option in number 22, please answer question 23 regarding your reaction to receiving the text messages, otherwise skip to 24:
- a. I did not find the SMS helpful.....True / False
  - b. I found the SMS helpful to remember to take medication.....True / False
  - c. I was worried that someone would see the SMS and discover my status .....True / False
  - d. The SMS helped me feel more connected to the hospital/my care provider.....True / False
  - e. The SMS helped me remember when my appointments were.....True / False
  - f. Someone other than me read one of the SMS and asked me about it.....True / False
  - g. A family member or friend discovered my HIV status because of the SMS.....True / False
  - h. The SMS gave me important information regarding my or my infant's care.....True / False
  - i. The SMS motivated me to continue PMTCT and/or EID care.....True / False
52. Please select a preference for frequency of ART adherence messages going forward:
- a. Never, please stop sending me adherence messages
  - b. Daily
  - c. Weekly
  - d. Every two weeks
  - e. Monthly

Thank you for your time and participation.

## Appendix IIC. 6 Month Postpartum survey (Intervention and Control Sites)

### For interviewer to fill out:

Study ID: \_\_\_\_\_

Date of interview \_\_\_\_\_

Interviewer initials \_\_\_\_\_

### Partner status & Disclosure

1. What is your **relationship status**?
  - a. Single
  - b. Married
  - c. Unmarried, but in a relationship
  - d. Separated
  - e. Divorced
  - f. Widowed
2. What is your **living situation**?
  - a. No current partner
  - b. Live separate from partner
  - c. Live with current partner
3. Who have you **disclosed your HIV status to**?
  - a. No one
  - b. Partner/husband
  - c. 1 or more family
  - d. 1 or more friends
  - e. 1 or more parent
4. What is your partner's HIV status?
  - a. HIV+
  - b. HIV –
  - c. Unknown
  - d. No current partner
5. Is your current partner the infant's father? ..... Y / N / NA
6. Who usually makes the final decision regarding how money is spent in your household?
  - a. My partner, always
  - b. My partner more often than me
  - c. My partner and me equally
  - d. Me more often than my partner
  - e. Me, always.
  - f. No current partner
7. Average weekly household income
  - a. Less than 500 KES
  - b. 500-750 KES
  - c. 750-1,000 KES
  - d. 1,000-2,500 KES
  - e. >2,500 KES
8. I worry that I will not have enough money to reach the hospital for my own or my child's care?
  - a. Strongly agree
  - b. Agree
  - c. Disagree
  - d. Strongly Disagree

### Partner Support (To be filled at 6 month VL test)

9. How often since your infant's birth has your male partner supported you in the follow ways:

|  |       |        |           |            |
|--|-------|--------|-----------|------------|
|  | Never | Rarely | Sometimes | Frequently |
|--|-------|--------|-----------|------------|

|  |  |  |  |  |
|--|--|--|--|--|
| 9a. Attended your child's medical appointments?                        |  |  |  |  |
| 9b. Provided money for transport to the hospital?                      |  |  |  |  |
| 9c. Gave you advice on infant feeding or hygiene?                      |  |  |  |  |
| 9d. Helped you with household responsibilities so that you could rest? |  |  |  |  |
| 9e. Reminded you to give your child medication?                        |  |  |  |  |
| 9f. Reminded you to take your medication?                              |  |  |  |  |
| 9g. Reminded you of the importance of following doctor's instructions? |  |  |  |  |
| 9h. Provided money to purchase medication or vitamins?                 |  |  |  |  |
| 9i. Provide encouragement to live a healthy life?                      |  |  |  |  |
| 9j. Pray together for the health of your family?                       |  |  |  |  |

### Depression

Please check the answer that comes closest to how you have felt IN THE PAST 7 DAYS, not just how you feel today.

10. I have looked forward with enjoyment to things
  - a. As much as I ever did
  - b. A little less than I used to
  - c. Much less than I used to
  - d. Not at all
11. I have blamed myself unnecessarily when things went wrong?
  - a. Yes, often
  - b. Yes, some of the time
  - c. Not very often
  - d. No, never
12. I have felt scared or panicky for no very good reason
  - a. Yes, quite a lot
  - b. Yes sometimes
  - c. No, not much
  - d. No, not at all
13. I have been so unhappy that I have been crying
  - a. Yes, most of the time
  - b. Yes, quite often
  - c. Only occasionally
  - d. No, never
14. The thought of harming myself has occurred to me
  - a. Yes, often
  - b. Sometimes
  - c. Hardly ever
  - d. Never

### Risk of Violence

For each of the following statements (15-18), choose the answer which best indicates how often each has occurred in the past 12 months

|   | Never | Rarely | Sometimes | Frequently |
|---|-------|--------|-----------|------------|
| 15. In the past 12 months, has your partner ever insulted you or made you feel bad about yourself?                          |       |        |           |            |
| 16. In the past 12 months, has your partner ever hit you, kicked you, dragged you, or beaten you up?                        |       |        |           |            |
| 17. In the past 12 months, has your partner ever hit, kicked, dragged or beaten your child?                                 |       |        |           |            |
| 18. In the past 12 months, has your partner ever physically forced you to have sexual intercourse when you did not want to? |       |        |           |            |

### PMTCT Knowledge

19. With what frequency should HIV+ mothers with undetectable viral loads receive a viral load test while they are breastfeeding their baby?
- Every 3 months
  - Every 6 months
  - Every 12 months
  - Only after their infant has stopped breastfeeding
20. When should HIV+ mothers stop taking their ART?
- Not until the infant begins eating solid food, at around 6 months.
  - Not until the infant stops breastfeeding.
  - Not until the infant has been confirmed HIV-negative at 18 months of age
  - Never, the mother should continue lifelong ART for her own health.
21. It is recommended that babies continue being routinely tested for HIV until when:
- 6 months of age
  - 12 months of age
  - 18 months of age
  - 2 years of age
  - The baby stops breastfeeding

#### PMTCT Motivation

For each of the following, indicate the extent to which you agree or disagree with the statement.

SD=strongly disagree, D=disagree, N=neither agree nor disagree, A= agree, SA = strongly agree.

|   | SD | D | N | A | SA |
|---|----|---|---|---|----|
| 22. I know I can maintain perfect adherence to my medication while my baby is very young and breastfeeding.                       |    |   |   |   |    |
| 23. Giving my baby his/her medication is extremely important to his health  |    |   |   |   |    |
| 24. Even if s/he does not want to take it, I know that I'll be able to give every dose of his/her medication                      |    |   |   |   |    |
| 25. It is extremely important to get routine viral load tests while my baby is still breastfeeding.                               |    |   |   |   |    |
| 26. Other commitments – such as work, household duties, childcare – may prevent me from getting my baby tested by 6 weeks of age. |    |   |   |   |    |
| 27. Attending all of my child's appointments is extremely important to me.  |    |   |   |   |    |

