### Objective 1 specific methods:

**Evaluate the efficacy of HITSystem 2.1 to increase the proportion of womens who receive complete PMTCT services through 6 m postpartum, per Kenyan guidelines.**

**Objective 1 outcomes.** The primary outcome for Objective 1 is the proportion receiving "complete PMTCT," an aggregate measure incorporating the documented receipt of all

designated services across the 3 PMTCT phases: maternal ART initiation, antenatal appointment attendance, facility delivery, EID linkage by 7 weeks of age, maternal VL testing and clinical action per national

Table 6. Aim 1 primary outcome: Services required for "complete PMTCT"

| Antenatal  | Delivery                | Postpartum (through 6m)   |
|--|-------------------------|---|
| 

• ART initiation

• On-time appointment attendance

• VL testing per guidelines

• Clinical action upon detectable VL

 | Hospital-based delivery | 

• EID linkage by 7 weeks

• VL testing per guidelines

• Clinical action upon detectable VL

 |

guidelines through 6 months postpartum (Table 6). Participants who receive all indicated services per guidelines will be coded as 1 or 'yes'. Participants missing  $\geq 1$  service will be coded as 0 or incomplete PMTCT services.

**Secondary outcomes** associated with Objective 1 will include gestational week at PMTCT enrollment, duration of PMTCT retention (weeks), and ART adherence (proportion >95%, proportion with missing/late prescription refill). Proportions will be calculated to describe each component of "complete PMTCT" separately (appointment attendance, VL monitoring, hospital delivery, EID linkage). Patient and facility-level factors will be assessed for their moderating impact on complete PMTCT. Provider characteristics will be aggregated and treated as facility-level variables. To assess pathways through which the HITSystem 2.1 works, we will measure provider and patient information and motivation as potential mediators

both pre- and post-intervention, and across study arms. Preterm births and infant weight at birth will be documented. We also will measure the proportion and timing/age of any HIV transmissions to infants, and maternal and/or infant deaths.

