**Statistical analyses for objective 1 (complete retention).** Data from women who have a documented reason for incomplete care at the study hospital (e.g. transfer facility, pregnancy loss, maternal death) will not be included in analyses. To demonstrate the efficacy of HITSytem 2.1 versus SOC, we will test for differences between arms by modeling complete PMTCT as a function of study arm and selected covariates (e.g., age, partner support, depression) using logistic mixed models with a random site intercept (to adjust for clustering). In post hoc analyses we will explore patient and facility-level characteristics as potential moderators of the effect of HITSytem 2.1, and examine changes in key individual level factors (disclosure status, partner status, depression, partner support) at the midpoint (delivery) and again at the end (6m postpartum). To assess mediating factors, we will compute average levels of provider knowledge and motivation for each site at baseline and end of study. These knowledge and motivation scores, as well as patient knowledge and motivation levels, will be compared pre-post intervention and between study arms to assess change within and between sites. In addition, provider and patient knowledge and motivation will be examined as predictors of PMTCT completion using logistic regression.

[figure not shown]

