## Appendix IIB. Delivery survey (within 4 weeks, Intervention and Control Sites)

### For interviewer to fill out:

Study ID: \_\_\_\_\_

Date of interview \_\_\_\_\_

Interviewer initials \_\_\_\_\_

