**Motisha wa uzungativu kwa taratibu za Kumkinga mtoto dhidi ya maambukizo toka kwa mama (PMTCT)**

Tafadhali changua jibu linaloonyesha kiwango ambacho unakubaliana au kutokubaliana na kila sentensi zifuatazo..

|   | Sikubaliani Kabisa | Sikubaliani | Sina Maoni | Nakubaliana | Nakubaliana kabisa |
|---|--------------------|-------------|------------|-------------|--------------------|
| 22. Najua naweza kudumisha uzingativu wa umesaji dawa ipasavyo, wakati mtoto wangu ni mchanga na ananyonya                                      |                    |             |            |             |                    |
| 23. Kumpa mtoto wangu dawa yake ni muhimu sana kwa afya yake  |                    |             |            |             |                    |
| 24. Hata ikiwa haipendi, najua kuwa nitaweza kumpa kulingana na kipimo cha dawa yake  |                    |             |            |             |                    |
| 25. Ni muhimu sana kupata vipimo vya upimaji wa kiwango cha virusi kitaratibu, wakati mtoto wangu bado ananyonya.                               |                    |             |            |             |                    |
| 26. Majukumu mengine – Kama kazi, shughuli za nyumbani, kushughulikia watoto – zinaweza kunizuia kumfanyia mwanangu upimaji, afikishapo wiki 6. |                    |             |            |             |                    |
| 27. Kuhudhuria taratibu zote za kliniki za mtoto wangu ni muhimu sana kwangu  |                    |             |            |             |                    |

|  | Sikubaliani Kabisa | Sikubaliani | Sina Maoni | Nakubaliana | Nakubaliana kabisa |
|--|--------------------|-------------|------------|-------------|--------------------|
|--|--------------------|-------------|------------|-------------|--------------------|

|   |  |  |  |  |  |
|---|--|--|--|--|--|
| 28. Nilikuwa na wasiwasi kuwa kuja hospitalini kwa upimaji wa watoto kunaweza kutuweka hatarini, mimi na mtoto kuambukizwa na COVID-19  |  |  |  |  |  |
| 29. Changamoto za kusafiri kwenda na kutoka hospitalini (gharama na / au upatikanaji wa magari) kwa sababu ya COVID-19 ilinifanya kuchelewesha au kukosa kuhudhuria miadi ya baada ya kujifungua. |  |  |  |  |  |
| 30. Nilichelewesha au nilikosa miadi ya baada ya kujifungua kwa sababu nilikuwa najisikia vibaya na sikutaka kuhatarisha wengine kwa ugonjwa.   |  |  |  |  |  |

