#### PMTCT Motivation

Kuom weche gi, ere ma iyiego kata idagi.

SD=strongly disagree, D=disagree, N=neither agree nor disagree, A= agree, SA = strongly agree.

|   | Adagi Ahinya | Adagi | Man e diere | Ayie | Ayie Ahinya |
|---|--------------|-------|-------------|------|-------------|
| 22. Angeyo ni anyalo luwora kod thieth kaka dwarore seche ma nyathina pod tin kendo dhoth           |              |       |             |      |             |
| 23. Miyo nyathi yathe en gima maber kuoma   |              |       |             |      |             |
| 24. Kata ka nyathi ok dwa yath, to angeyo ni abiro miye yath kaka dwarore                           |              |       |             |      |             |
| 25. Ber mondo nyatho oyud pim mar viral seche duto ndalo mapod odhoth                               |              |       |             |      |             |
| 26. Dich moko machalo kaka tich, tije ot, rito nyathi nyalo mona mondo oyud pim mar dweche auchiel. |              |       |             |      |             |
| 27. Tero nyathi e thieth seche madwarore en gima ger ahinya   |              |       |             |      |             |

|  | Adagi ahinya | Adagi | Man e dierel | Ayie | Ayie Ahinya |
|--|--------------|-------|--------------|------|-------------|
| 28. Chunya chandre ni ka atero nyathina e pim e od thieth to wanyalo yudo tuo mar covid -19  |              |       |              |      |             |
| 29. Weche mag wuoth dhi kendo duogo ka aa e od thieth(weche pesa kata yudo gari/apiko) kalure kod tuo mar covid 19 ne omiyo adeko, kata koso yudo thieth |              |       |              |      |             |
| 30. Ne adeko yudo thieth kata dhi e od thieth mondo,nikech ne atuo kendo ne ok adwa ni mondo ami ji tuo  |              |       |              |      |             |

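### Item 26 of the 6-month survey asks prospectively about a 6-week infant test already past, and the Luo form names a different test, so it should not enter the motivation score

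*Combined protocol and SAP*

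**What the plan says.** Appendix IIB is the delivery form, titled "Delivery survey (within 4 weeks, Intervention and Control Sites"). Its fifth motivation item reads "32. Other commitments – such as work, household duties, childcare – may prevent me from getting my baby tested by 6 weeks of age". Appendix IIC, the 6-month form, prints the same six motivation statements as items 22 to 27, and the fifth is again "26. Other commitments – such as work, household duties, childcare – may prevent me from getting my baby tested by 6 weeks of age".

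The translations of the 6-month item differ. Swahili (Kiambatisho IIC) ends "kumfanyia mwanangu upimaji, afikishapo wiki 6", which is six weeks. Luo ends "nyalo mona mondo oyud pim mar dweche auchiel", which is six months, although the Luo delivery form refers to six weeks.

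Under Objective 1 specific methods, complete PMTCT requires every service in Table 6, including "EID linkage by 7 weeks of age", and a woman who misses any one is coded 0. The analysis paragraph compares patient knowledge and motivation before and after the intervention and between arms, and adds that "provider and patient knowledge and motivation will be examined as predictors of PMTCT completion using logistic regression". The Participant surveys paragraph gives mediation and moderation as the reason for repeating the measures. Objective 2 reuses the mediation methods. No passage says which wave supplies the patient predictor, how the items are combined, or whether item 26 is reverse-scored.

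**The concern.** A statement that something may prevent a test is a measure of expectation only while the test lies ahead. At six months the mother must answer from memory, hypothetically or not at all, so the item no longer measures what it measured at delivery. It also means something different on the Luo form.

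The analytic risk follows from the overlap with the outcome. Timely infant linkage is one of the eight services in Table 6. If a mother whose infant missed the early test tends to agree with item 26, and one whose infant was tested tends to disagree, the item partly records the outcome it is meant to explain. An association between 6-month motivation and completion could then appear with no effect of motivation. A shift in the score between delivery and six months could likewise reflect the test having happened rather than a change in motivation.

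**Working it through.** **1. Timing.** The delivery survey is taken by week 4, before a 6-week test. Six months is about 26 weeks, so item 26 is asked about 26 − 6 = 20 weeks after its date, roughly four and a half months.

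**2. Carry-over or intention?** The COVID question on infant testing is in the present and future at delivery and in the past tense at six months. The authors updated that item; item 26 was left alone. That points to a carry-over.

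**3. Languages.**

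| Form | Delivery, item 32 | 6 months, item 26 |
|---|---|---|
| English | 6 weeks | 6 weeks |
| Swahili | 6 weeks | 6 weeks |
| Luo | 6 weeks | 6 months |

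**4. Possible size.** The plan gives no figure to reproduce, so this is an illustration. From the documents: 2 × 6 × 75 = 900 women analysed, and completion of about 12% and 32% (Table 3). Assumed: an equally weighted mean of six items, inter-item correlation 0.3, item 26 reverse-scored, true motivation unrelated to completion, and item 26 lower by d item-SDs when linkage was missed.

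- SD of the mean score, in item-SDs: √[(1 + 5 × 0.3)/6] = √0.417 = 0.645.
- Shift in the score when linkage is missed: (d/6)/0.645 = 0.26d score-SDs, which is 0.13, 0.26 and 0.39 for d = 0.5, 1 and 1.5.

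Logistic regression of completion on the score, without clustering, 200 simulated trials per setting, overall completion 12% to 32%, d = 0.5 to 1.5:

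| Linkage by 7 weeks | Odds ratio per SD (truth 1.0) | Significant at 5% |
|---|---|---|
| 90% | 1.01–1.06 | 3–14% |
| 80% | 1.04–1.13 | 6–41% |
| 70% | 1.04–1.19 | 6–65% |
| Any of these, d = 0 | 0.99–1.00 | 2–7% |
| Any of these, item 26 dropped | 0.99–1.02 | 3–9% |

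With 200 runs, a true 5% rate has a standard error of √(0.05 × 0.95/200) = 1.5 percentage points, so the last two rows are consistent with no bias. The last row is null by construction, because the other five items were simulated as unrelated to the outcome.

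**5. Less and more favourable inputs.** Here linkage differs by arm, completion is 12% and 32%, and the shift is in points on the 5-point scale (item SD about 0.9).

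- Linkage 60% against 70–80%, shift 1–2 points, every woman affected: odds ratio 1.10–1.29; significant in 28–89% of trials unadjusted and 22–87% adjusted for arm.
- Linkage 80% against 90%: significant in 6–26%.
- Linkage 60% against 70–80%, but only one third of women on an affected form: odds ratio about 1.04 and 6–7% for a 1-point shift; 1.06–1.08 and 11–17% for 2 points.

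The one-third figure is an assumption. Table 2 places 8 of 12 sites in Siaya; if women there used the Luo form, 4/12 of sites would carry the faulty wording. The documents give no split by language.

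**The case against.** The strongest reply is that this is a questionnaire slip in one item of a secondary measure, and that bias needs several unstated conditions together. The 6-month wave must supply the predictor; enrolment and delivery scores precede the 6-week date. The items must be combined into a patient score, whereas the plan describes averaged scores only for providers. Item 26 must be reverse-scored, or its contribution changes sign. Answers must track the event, yet a woman can still read the statement hypothetically, neutrally, or as a barrier she overcame. The item also speaks of testing by 6 weeks, while the outcome is linkage by 7 weeks. All of this stands, and it limits the claim to what can happen.

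A reader might infer that item 26 makes motivation a false predictor of completion, or that 6-month motivation will differ by arm even if the intervention changes nobody's motivation. The documents do not support that: no passage fixes the wave or the scoring, none shows that answers follow the test, and the overlap does not arise on the Luo form. The highest false-positive rates come from low linkage and large shifts applied to every woman.

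What the reply does not remove is the item itself. It is out of date in two languages and different in the third, whatever its effect on a model. Nor does the plan exclude the 6-month survey, which is the last patient measurement and the natural post-intervention one. Enrolment motivation items differ in content, so delivery to six months is the only pair of waves with matching English items.

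**Conclusion.** The instrument fault is established by the text: item 26 is invalid at six months in English and Swahili and not comparable with Luo. The consequence for analysis is conditional. If the 6-month items are scored together and used as mediator or predictor of complete PMTCT, and if answers reflect whether the test took place, the score carries part of the outcome. The distortion then ranges from negligible (high linkage, weak tracking, or mostly Luo forms) to material (linkage near 70% or lower with shifts of one SD or more). The documents supply none of these inputs.

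The reach is limited. The primary arm model gives age, partner support and depression as example covariates, not motivation, so the primary comparison is untouched. For Objective 2 the invalid item would still enter the mediation work, but viral load does not contain infant linkage, so the direct overlap is confined to Objective 1. Removing item 26 deals with this overlap only: any 6-month score is taken after most Table 6 services are finished, so reverse causation remains possible through the other items.

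**What to change.** For forms not yet used, reword item 26 to a test that is still ahead of the mother when she is asked, and name the same test in English, Swahili and Luo.

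For completed forms, leave item 26 out of the 6-month motivation score. When change from delivery is computed, leave out delivery item 32 as well, so that both waves use the same five items and form versions are not mixed. Two sites had already finished enrolling, so some 6-month forms may already have been completed.

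In the analysis plan, state the scoring rule, including reverse-coding, and the survey wave for each mediator and predictor model. Use enrolment or delivery motivation, and only for outcome components that fall due after that survey; delivery motivation, for example, can be related to infant linkage and postpartum viral load testing. If item 26 is reported at all, tabulate it by form language.

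The cost is one reworded statement, aligned across three languages, and a few lines of scoring text. The change score rests on five items instead of six, a small loss of reliability. Delivery motivation can no longer be presented as a predictor of the whole composite, because its antenatal and delivery components precede that survey.
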